9.5.3 Immunogenicity (Visits 3 to 5, 7 to 17)

The approximate volumes taken for immunogenicity testing are:

- VNTs (serum) (~18 ml). Blood will be taken at 12 visits.
- IgM/ IgG ELISA (serum) (~6 ml). Blood will be taken at 12 visits.
- Cell-mediated immune response and leukocyte phenotyping of PBMCs (~60 ml at baseline and ~40 ml at subsequent visits) – PBMCs will be taken for the first 5 subjects in Group 2 and all subjects in Groups 3 and 4. In addition, all 10 subjects receiving Rabipur® will be included. Blood will be taken at 6 visits.
- Cytokine assessment (serum) (~6 ml) – for the subjects in the CV7202 groups providing PBMCs. A total of 7 (or 8 for subjects receiving 2 doses of CV7202) blood samples will be taken at 6 visits.
- Transcriptome profiling (PBMCs) (~10 ml) – for the subjects in the CV7202 groups providing PBMCs for cell-mediated immune response and leukocyte phenotyping. Blood will be taken at 6 visits.
- Immune receptor sequencing (PAXgene DNA) (~5 ml). Blood will be taken at 8 visits.

In case a site visit is not possible due to the public health emergency related to COVID-19, the blood sample for immunogenicity assessments should be collected at Visits A, only in case restrictive measures related to COVID-19 no longer prevent site visits (refer to Sections 9.4.16 to 9.4.19 for details).

10 Statistical Considerations

Due to the exploratory nature of this trial only descriptive statistics will be used, no confirmatory statistical inference will be performed.

10.1 Sample Size Determination

No statistically-based sample size estimation was performed.

10.2 Populations for Analyses

Safety set: This is the subset of subjects, who have received at least one dose of the candidate rabies mRNA vaccine CV7202 or the active control Rabipur® and for whom any post-Day 1 safety data are available. The statement that a subject had no AEs (on the Adverse Event eCRF) constitutes a valid safety assessment. The analysis of safety will be performed on this population.

Full-analysis (FA) set: This is the subset of the Safety Set with subjects who have the baseline sample and at least one additional blood sample available for VNT analysis. This analysis set is the primary analysis set for all immunogenicity objectives.

Per protocol (PP) set: This is defined as a subset of the FA set as follows:

1. PP1 = Subjects enrolled in Group 1 (Rabipur®) and Groups 2 to 4 who have received at least 1 administration of the trial product (including those to be selected for the second vaccination), have completed the Day 57 visit and for whom baseline through Day 57 immunological results (at least rabies VNTs) are available.
2. PP2 = Defined as a subset of PP1 comprised of subjects who have received two administrations of the trial product, have completed the Day 91 visit and for whom baseline through Day 91 immunological results (at least rabies VNTs) are available.

Any subject for whom substantive protocol deviations are documented will be excluded from the PP set. The following pre-defined major protocol deviations will lead to the exclusion from the PP set:

- Any deviation of the Inclusion/Exclusion criteria.
- Any trial subject that requires therapy listed as an exclusion criterion in section 6.2.
- Any trial subject that has not received the trial product on the scheduled date.
- Any trial subject for whom the immunological sample has been taken outside of the planned visit window.
- Pre-existing RABV-G specific immune response.

Further subgroup analyses may be defined and specified in the statistical analysis plan (SAP).

10.3 Statistical Analyses

10.3.1 General Considerations

All data obtained in this trial and documented in the eCRF will be listed and summarized with sample statistics or frequency tables as appropriate. In all tables, listings and figures the dose groups will be reported from the lowest to the highest dose, with the 'a' groups as separate columns.

A statistical analysis plan (SAP) will be prepared and finalized at the latest prior to database lock for the interim analysis. This document will provide further details regarding the definition of analysis variables and analysis methodology to address all trial objectives and the handling of missing data.

This trial is designed as an exploratory phase I trial with no confirmatory proof of hypotheses.

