| Table 2.2 | Staggered Enrolment and Dose Escalation for Groups 2 to 4 (Dose 1) with Minimum Time Intervals* | 16 |
| Table 8.1 | Protocol CV-7202-104 Dose regimen | 37 |
| Table 9.1 | Intensity Grading for Solicited Local AEs (Days 1 to 8) | 39 |
| Table 9.2 | Intensity Grading* for Solicited Systemic AEs (Days 1 to 8) | 40 |
| Table 9.3 | Timing and Maximum Volumes of Blood Draws | 54 |
| Table 12.1 | Protocol-Required Safety Laboratory Assessments | 73 |
| Table 12.2 | List of Names and Addresses | 74 |

List of Figures

| | | |
|------------|--------------------------------|----|
| Figure 5.1 | CV-7202-104 Trial Design | 23 |
|------------|--------------------------------|----|

1 Synopsis

| | |
|---|--|
| Protocol Title: | A non-randomized, open label, controlled, dose-escalation, phase I clinical trial to evaluate the safety, reactogenicity and immunogenicity of one or two administrations of candidate rabies mRNA vaccine CV7202 in healthy adult subjects |
| Short Title: | Safety, reactogenicity and immunogenicity of CV7202 in healthy adult subjects |
| Rationale: | The objectives of this phase I trial are to assess the safety and reactogenicity of CV7202 in the context of immune responses to rabies virus glycoprotein (RABV-G) in order to select the optimal dose and number of doses. The dose range selected is intended to provide data for defining the optimal dosage of CV7202 to be tested in subsequent clinical trials. |
| Sponsor: | CureVac AG [name] [name] Germany |
| Coordinating/Principal Investigator: | |

Trial Objectives and Endpoints:

| Objectives | Endpoints |
|--|--|
| Primary | |
| 
To assess the safety and reactogenicity profile of CV7202 administered intramuscularly (i.m.) to healthy adults (18–40 years old), as a range of doses (1, 2 and 5 µg) in one- or two-dose regimens. | 
The percentages of subjects with, and the frequencies and intensities of solicited local adverse events (AEs) reported on the day of vaccination and the 7 subsequent days (Days 1–8). |
| | 
The percentages of subjects with, and the frequencies, intensities and relationship to vaccination, of solicited systemic AEs reported on the day of vaccination and the 7 subsequent days (Days 1–8). |
| | 
The duration (in days) of solicited local AEs, of solicited systemic AEs and of the individual solicited AEs. |

| | |

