5.1.2 Stopping Rules

For dose escalation (group)

At each planned safety review, safety data will be reviewed and a GO/NO GO decision made accordingly for enrolment of further subjects and administration of subsequent doses.

Enrolment or administration at the given dose level will be temporarily halted and only continued after DSMB approval and approval by the competent authority following the occurrence of:

- Any related SAE in the opinion of the principal investigator (PI), the DSMB and/or the iSRC.
- Related severe AEs of the same kind in $\geq 20\%$ of the subjects in one group with the following exceptions:
 - Transient grade 3 chills, fatigue, headache, fever, myalgia or arthralgia resolving within 24 hours to grade ≤ 2 .
 - Transient grade 3 local AEs reducing to grade ≤ 2 within 48 hours.

Based on the review of the data, the DSMB will decide about temporary or permanent stopping of dosing in the given and eventually also lower dose groups (pertaining to the 2nd dose administration). After a temporary halt further measures for safety monitoring (i.e. additional safety visits including safety blood sampling at additional time points) may also be introduced based on DSMB recommendation.

For further CV7202 dose administration (subject)

Subjects must not receive a second dose of CV7202 in the event of:

- Occurrence of an allergic/anaphylactic reaction after the first dose.
- Any related SAE in the opinion of the PI, the DSMB and/or the iSRC.
- Any related severe (grade 3) AEs with the following exceptions:
 - Transient grade 3 chills, fatigue, headache, fever, myalgia or arthralgia resolving within 24 hours to grade ≤ 2 .
 - Transient grade 3 local reactions resolving to grade ≤ 2 within 48 hours.

If these reactions occur, the subject must not receive additional vaccinations but is encouraged to continue in trial participation for safety reasons, including collection of safety blood samples. Immunogenicity assessments may be performed at the investigator's discretion and if the subject agrees.

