8.4 Trial Groups

The subjects will be distributed among the different groups to receive CV7202 or Rabipur® (Table 8.1).

Table 8.1 Protocol CV-7202-104 Dose regimen

| | Trial Product | Composition | Dosing | | |
|--------------------------------|---------------|-------------|--------|-------|--------|
| | | | Day 1 | Day 8 | Day 29 |
| | | | N | N | N |
| Group 1 | Rabipur® | N/A | 10 | 10 | 10 |
| Group 2* | CV7202 | 5 µg mRNA | 10 | N/A | N/A |
| Group 3 • Group 3a** | | 1 µg mRNA | 16 | | 8 |
| Group 4 • Group 4a** | | 2 µg mRNA | 16 | | 8 |
| Total CV7202 | | | 42 | | 16 |

* Note that enrolment in Group 2 was already completed at the time this protocol amendment was issued.

** 'a' groups are a subset consisting of 8 subjects of Groups 3 and 4 scheduled to receive a first dose on Day 1 and a second dose on Day 29.

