6. GENERAL ANALYSIS CONSIDERATIONS

The statistical analyses will be reported using summary tables, listings, and figures (TLFs). The International Council for Harmonisation (ICH) numbering convention will be used for all TLFs. Due to the exploratory nature of this trial, only descriptive statistics will be used; therefore, no confirmatory statistical inference will be performed.

Continuous variables will be summarized with means, standard deviations, medians, minimums, maximums, and valid cases. Other summaries may be used as appropriate.

Categorical variables will be summarized by counts and by percentage of subjects in corresponding categories. Percentages for missing values are omitted and do not account for the percent calculation of other categories. Percentages are routinely based on the total category count excluding the missing category if not otherwise mentioned. Percentages showing a rate relative to the total number of subjects in this group are given in special tables (eg, adverse event [AE] tables). Footnotes will specify the percent basis in those cases.

All summary tables will be presented by vaccination group (in the tables denoted as 'dosage/vaccine'). Baseline summaries will also include a total summary column. The CV7202 dose groups will be reported from the lowest to the highest dose. Selected tables will also display by dose regimen (in the tables denoted as 'treatment group').

Individual subject data obtained from the eCRFs or data from external sources like immunogenicity laboratory data and any derived data will be presented by subject in data listings. All post-baseline unscheduled assessments will be listed only. Only scheduled post-baseline safety measurements will be summarized, if appropriate. Should a repeat occur at a scheduled visit then only the last result per visit will be considered for the summary tables.

The analyses described in this plan are considered a priori, in that they have been defined prior to database lock. Any analyses performed subsequent to finalization of this statistical analysis plan will be considered post hoc and exploratory. Post hoc analyses will be labeled as such on the output and identified in the clinical trial report.

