Arthralgia	2	Moderate, some interference with normal activity
	3	Significant, prevents normal activity
	0	Absent
Nausea/ Vomiting	1	Mild, no interference with normal activity
	2	Moderate, some interference with normal activity
	3	Significant, prevents normal activity
Diarrhea	0	Absent
	1	2 or 3 loose stools or <400 g/24 hours
	2	4 or 5 stools or 400 – 800 g/24 hours
	3	6 or more watery stools or >800 g/24 hours or requires outpatient i.v. hydration

*United States Food and Drug Administration toxicity grading scale; i.v. = intravenous.

Solicited AEs are also documented as AEs on the respective eCRF pages by the investigator, if they are serious and/or are ongoing on Day 8.

For every solicited AE, the maximum over all grades documented in the diary on the day of vaccination and the 7 subsequent days will be defined as grade (intensity) of this solicited AE.

Frequencies and percentages of local and systemic solicited AEs reported on the day of vaccination and the 7 subsequent days will be displayed by vaccination group, by subject overall and vaccination dose (number).

An overall summary table will display frequencies and percentages by grade (intensity) including any grade of:

- Any solicited AEs
- Local solicited AEs

- Systemic solicited AEs
- Related systemic solicited AEs
- Any solicited AEs ongoing on Day 8

Frequencies and percentages by grade (intensity), including any grade, will also be displayed for the individual terms of solicited AEs. Gradings of zero (AE is absent) will not contribute to the numbers tabulated.

The duration in days of a solicited AE will be represented by the number of days with diary entries of Grade ≥ 1 (out of Days 1-8) reported by a subject per solicited AE term and diary (corresponding to vaccination dose). Thus, the duration in days can range from 1 to 8 per prespecified solicited event term and vaccination dose administered.

The duration of Grade 3 solicited AEs will be derived by counting only days with Grade 3 entries.

For subjects without a specified event term, no duration of this event will be calculated, ie, no zero durations are possible.

The number of days of solicited AEs, as well as the number of days of solicited Grade 3 AEs will be tabulated with basic statistics by vaccination group and vaccination dose (number) for any solicited AE, any local solicited AE, any systemic solicited AE, any related systemic solicited AE, and the individual terms of solicited AEs.

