11.2.2 Unsolicited Adverse Events

Serious AEs, intercurrent medical conditions, AEs leading to trial or vaccine withdrawal, AEs of special interest (AESIs) and MAAEs will be collected by the investigator in the eCRF throughout the trial.

AEs with a suspected potential immune-mediated disease etiology will be considered AESIs. The investigator will assess if an AE is an AESI. A list of AESIs is provided in Appendix 10 of the protocol.

AEs that are reported as related to the test vaccine will be considered trial vaccine-related; missing classifications concerning trial vaccine relationship will also be considered trial vaccine-related.

Every unsolicited AE will be assigned to a vaccination dose (number) by consideration of the period of 28 days after vaccination administration. Unsolicited AEs can be assigned to either day 1 to 28 (dose 1 for any vaccination group), or day 29 to 57 (dose 2 for 2-dose regimens or dose 3 for the Rabipur group). For the Rabipur group, vaccination dose 2 is administered 8 days after vaccination dose 1, therefore no assignment of unsolicited AEs to vaccination dose 2 is done for the Rabipur group.

All AE summaries will be restricted to those AEs that occurred after the first administration of the trial product. Any other AE (ie, AE starting after trial entry and before the first vaccination) will be reflected only in the data listings. If it cannot be determined whether the AE occurred after the first administration of the trial product due to a partial onset date, then it will be counted as such. Verbatim terms in the eCRFs will be mapped to preferred terms (PTs) and system organ classes (SOCs) using the Medical Dictionary for Regulatory Activities (version 21.0 or higher).

The occurrence of unsolicited AEs reported on the day of vaccination and the 28 subsequent days will be presented. In addition selected AE summary tables will be repeated for unsolicited AEs occurring at any time after the first administration of the trial product.

Each AE summary will be displayed by vaccination group and dose regimen. Summaries by vaccination dose (number) will also be provided for all AEs. Summaries that are displayed by SOC and PT will be ordered by descending order of incidence of SOC and PT within each system organ class. Summaries will display number and percentage of subjects with at least 1 event and the number of events by vaccination group.

Summaries of the following types will be presented:

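### Nine any-dose adverse event shells lack the two-dose ('a' group) columns that protocol 10.3.1 requires, so the 7-day and 28-day shells do not show the cumulative adverse event rate by regimen

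*Protocol*

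**What the plan says.** **Protocol.** Section 10.3.1 states, for all tables, listings and figures, that "the dose groups will be reported from the lowest to the highest dose, with the 'a' groups as separate columns". The footnote to Table 8.1 explains that the 'a' "groups are a subset consisting of 8 subjects of Groups 3 and 4", namely those scheduled for a second dose on Day 29.

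**SAP text.** Section 6 says "All summary tables will be presented by vaccination group" and then "Selected tables will also display by dose regimen". Section 11.2.1 plans the solicited tables by dose level, over all doses and for each dose separately, and does not mention regimen. Section 11.2.2 goes further for unsolicited events: "Each AE summary will be displayed by vaccination group and dose regimen". Section 12 declares one change from the protocol, the dropped per-protocol sets.

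**SAP shells.** Appendix C lists treatment-group versions of the disposition, demographic, baseline, VNT, immunoglobulin and investigator site-reaction tables. It lists none for the nine AE shells at issue here.

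**The concern.** The trial assesses safety alongside immune response "in order to select the optimal dose and number of doses", and its primary objective is safety in one- and two-dose regimens. A subject given two doses has two chances of an event, so an any-dose rate pooled over both regimens describes neither. Suppose, purely as an illustration, a risk of 30% per dose, independent between doses. The two-dose any-dose rate is then 1 − 0.7² = 51%, the one-dose rate is 30%, and the pooled column shows (8 × 30% + 8 × 51%)/16 = 40.5%. The analysis is descriptive throughout, so the tables are the result. The number of doses would then be chosen without a table that sets the cumulative AE burden of one dose beside that of two.

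**Working it through.** **1. Inputs.** Protocol Table 8.1 gives 10 + 16 + 16 = 42 CV7202 subjects on Day 1 and 8 + 8 = 16 on Day 29, which matches its printed totals. Each of the 1 µg and 2 µg columns therefore holds 16 subjects, 8 per regimen as planned. The 5 µg and Rabipur groups each have a single regimen and are not affected.

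**2. Count of any-dose AE shells (SAP Appendix D1).** Repeat-table notes are followed to the parent shell.

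| Window | Pooled columns only | Regimen columns |
|---|---|---|
| 7 days, solicited | 14.3.1.1.1.1, .5, .9, .13 | none |
| 28 days, unsolicited | 14.3.1.2.1, .4, .5 | none |
| Whole trial, unsolicited | 14.3.1.3.1, .3 | 14.3.1.3.2 (without 5 µg and Rabipur) |

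Nine of ten are pooled, including all seven in the 7-day and 28-day windows.

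**3. What other tables show.** The Post Dose 2 shells (for example 14.3.1.1.1.3 and .7, 14.3.1.2.3 and .7) have 2x1 µg and 2x2 µg columns, so reactions to the second dose are shown as observed. The corresponding 7-day and 28-day Post Dose 1 shells are pooled.

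**4. Can the 7-day and 28-day regimen rates be recovered?** For an any-grade row at one dose level, let D1 be the subjects with an event after Dose 1 (of 16), D2 those after Dose 2 (of 8) and A those after any dose (of 16). One-dose subjects cannot add to A beyond D1, so b = A − D1 two-dose subjects were first affected after Dose 2. Let a be the two-dose subjects with a Dose 1 event. The two-dose count is a + b, but a is not shown. The tables only bound it:

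max(0, D1 − 8, D2 − b) ≤ a ≤ min(8 − b, D1).

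Illustration: D1 = 8, D2 = 4, A = 10 gives b = 2 and a from 2 to 6. The two-dose rate is then anywhere from 4/8 to 8/8, and the one-dose rate correspondingly from 6/8 down to 2/8.

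If both subsets have the same Dose 1 rate, the two-dose rate can be estimated as D1/16 + (A − D1)/8, here 8/16 + 2/8 = 75%. Its error against the observed rate is a/8 − D1/16. With exchangeable subsets, a is hypergeometric with variance 8 × (D1/16) × (1 − D1/16) × (8/15):

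| D1 | SD of a (subjects) | SD of error (points) |
|---|---|---|
| 2 | 0.683 | 8.5 |
| 4 or 12 | 0.894 | 11.2 |
| 8 | 1.033 | 12.9 |

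The formula does not apply to single-grade 1 and 2 rows. Subjects are counted once at their highest grade, so a worse second-dose reaction can make A smaller than D1.

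**5. Is the equal-rate condition secured?** No. The trial is non-randomized (protocol 8.5) and regimen is analysed as received (SAP 7). Protocol 5.1.2 also states: "Subjects must not receive a second dose of CV7202 in the event of" a related SAE, or a related grade 3 AE outside the listed transient exceptions. If, for illustration, two subjects were barred for such a grade 3 AE and nobody reacted to Dose 2, the formula gives 2/16 = 12.5% for both regimens. The observed rates would be 2/8 = 25% (one dose) and 0/8 (two doses).

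**6. Whole-trial tables.** Shell 14.3.1.3.4 has 1x1 µg and 1x2 µg columns, so subtracting it from 14.3.1.3.3 gives the two-dose counts exactly. Shell 14.3.1.3.2 covers all and related AEs by regimen. That leaves 8 − 2 = 6 rows of 14.3.1.3.1: SAE, related SAE, MAAE, withdrawal from study, discontinued vaccination and AESI. These have no regimen column and no whole-trial Post Dose 1 counterpart, so step 4's estimate is not available either.

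**The case against.** The case for leaving the shells alone has substance. All 16 subjects at a dose level receive the same first dose, so a pooled Post Dose 1 table is a sensible summary. Second-dose reactogenicity is already shown by regimen. SAP 6 openly limits regimen display to selected tables, SAP 11.2.2 plans it in words for unsolicited events, and Appendix A lets tables be split during programming. With D1 = 8 and exchangeable subsets, before conditioning on the Post Dose 2 count, the estimate is within one subject of eight with probability (2 × 56² + 70²)/12870 = 11172/12870 = 87%. Regimen columns as received can also mislead: in the 25% against 0% example, the contrast comes from who was allowed a second dose.

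These points narrow the concern to the cumulative rate. They do not remove the departure, which SAP 12 leaves undeclared. Small columns are a weak defence, because the SAP already tabulates VNT and investigator-assessed site reactions for the same groups of 8.

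A reader might infer more than the documents support:

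- **That pooling is itself the breach.** The 'a' groups are subsets and SAP 6 keeps the vaccination-group columns. The fault is the missing 'a' columns.
- **That the primary SAE, MAAE and AESI endpoints are lost.** Those endpoints run to 12 months, whereas 14.3.1.3.1 covers the whole trial and is not their exact table.
- **That all grade 3 rows are distorted by selection.** They also count exempt transient reactions, after which Dose 2 is allowed, so only part of each row is affected. For related SAEs known before Dose 2, the bar applies directly. No passage reports that anyone was barred.

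**Conclusion.** The point holds and should be acted on. Nine shells omit columns that protocol 10.3.1 requires. The five unsolicited ones also conflict with SAP 11.2.2, while the four solicited ones agree with SAP 6 and 11.2.1 and depart only from the protocol. The consequence is limited to the cumulative any-dose rate by regimen at 1 µg and 2 µg in seven 7-day and 28-day tables, plus six rows of 14.3.1.3.1. Nothing is lost in 14.3.1.3.3.

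The error sizes assume 8 subjects per regimen and subsets exchangeable before Dose 2. The AE counts are invented for illustration. The subject-level listings (16.2.7.1.1, 16.2.7.2.1 and .2) hold the data, so this is a reporting gap and not a loss of information from the trial.

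**What to change.** - Keep the pooled columns. Add 1x1, 2x1, 1x2 and 2x2 µg columns, or companion treatment-group tables as already done in 14.3.5.2 and .4, to 14.3.1.1.1.1, .5, .9 and .13, to 14.3.1.2.1, .4 and .5, and to 14.3.1.3.1. For 14.3.1.3.3 this is for consistency only.
- Add 5 µg and Rabipur to 14.3.1.3.2.
- Footnote the regimen columns: regimen is as received, with the number of subjects not given Dose 2 under protocol 5.1.2.
- State in one SAP 12 sentence that the remaining tables stay pooled, as a departure from protocol 10.3.1.

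The cost is shell edits and that sentence. The regimen labels exist in SAP 7 and no new data are needed. The downside is columns of 8 subjects (an observed 4/8 has an exact 95% interval of 15.7% to 84.3%) and the as-received selection, which the column sizes and the footnote disclose.
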